8.2.2.3. Determine the safety/tolerability of the qHPV and 9vHPV vaccine in cancer survivors

In the IT sample, the number of vaccine-associated AE within 7 (for 9vHPV) or 14 (for qHPV) days of each dose will be compared to those reported for the age- and sex-matched general population: % of subjects with injection site AEs (e.g., pain, erythema), % of subjects with systemic AEs (e.g., fever, syncope, headache, hives, rashes, diarrhea), % of subjects with serious AEs (e.g., life-threatening, result in persistent disability or death). Overall cohort: % of subjects who discontinue vaccine related to AE. AEs will be summarized descriptively as frequencies and percentages by type (injection site, systemic, serious), by vaccine dose (i.e., #1, #2, #3), and across all vaccine doses. Chi-square and exact tests will be used for comparison depending on the rarity of events. Our smallest PP subsample of 72 young females will provide 80% power to detect a difference of 0.0485 in AE rates if true rate=0.01, and a difference of 0.1068 if the true rate=0.85. For the largest PP subsample of 82 young males, the corresponding detectable differences are 0.0415 and 0.1021. For the entire PP sample of 312, the corresponding differences are 0.0189 and 0.0534. Type I error=.05 is assumed for each comparison.

8.2.2.4. (Exploratory sub-aim): Evaluate the persistence of antibody response at 2 years post vaccine initiation and identify clinical/host factors influencing response persistence.

Outcome measure (GMT): We will calculate mean GMT and 2-sided 95% CI for HPV-16 and -18 at Month 24 following vaccine initiation for PP subjects and compare them to age-, sex-, and time-matched means in the historical healthy population.²⁸ Cancer survivors will be considered to have non-inferior persistence of antibody response to a subtype at a time point if the lower 95% confidence limit for the ratio of GMT in cancer survivors to historical healthy population is $\geq 50\%$.³⁰

Outcome measure (seropositivity): Seropositivity is defined as: qHPV cohort: Anti-HPV-6, -11, -16, and -18 titer $\geq 20, 16, 20,$ and 24 mMU/ml respectively;³⁰ 9vHPV cohort: Anti-HPV-6, -11, -16, -18, -31, -33, -45, -52, and -58 titer $\geq 30, 16, 20, 24, 10, 8, 8, 8,$ and 8 mMU/ml, respectively.⁶⁹ Among PP participants, the percent seropositive to each vaccine subtype will be computed and compared to age- and sex-matched seropositive rates at Month 24 in the healthy population.²⁸ One-sided tests of noninferiority for each HPV type will be conducted at the 0.025 (multiplicity adjusted) level according to the methods of Miettinen and Nurminen.¹³⁷ For each subtype and time point, persistence of seropositivity will be considered non-inferior in cancer survivors if the lower 95% CI for the difference in percent seropositivity between the healthy and cancer population is less than 5 percentage points. To identify factors associated with response persistence at each time point, we will classify cancer survivors as having impaired response persistence if their GMT is lower than $\frac{1}{2}$ of the mean GMT in the age-sex-time matched healthy population. Logistic regression will be conducted at each time point to identify significant predictors of impaired response persistence. Potential predictors include sex, primary diagnosis, current age, age at diagnosis/HCT, prior therapy (all therapeutic exposures, including cumulative doses of all immunosuppressive agents), intensity of therapy (conventional therapy vs. HCT), time from completion of therapy, presence and extent of chronic GvHD, and Day 1 Quant Ig. In this exploratory sub-aim, we will also measure HPV-specific total immunoglobulin (total Ig) at Month 24 to better characterize the qualitative aspects of the HPV-specific humoral immune response.^{138,139} We recognize that we may not have sufficient power to test persistence of response to qHPV or 9vHPV vaccine; as such, this aim is exploratory.

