6.7 Financial Obligations and Compensation

There is no charge for participation in this study. Vaccines and related preparation and administration charges and all study-related labs will be provided without cost to the participant. To compensate Aim 2: Vaccine Evaluation participants for their time and transportation expenses related to study participation, participants will receive \$100 (or equivalent voucher/gift card) at Month 7 and \$75 (or

equivalent voucher/gift card) at Month 24.

6.8 **Informed Consent Process**

Informed consent will be obtained from each patient (of age of majority) according to the approved procedures of the institutional review board (IRB) or Ethics Committee at each participating institution. Consent of the parent/guardian and assent of the patient will be obtained for each minor participant according to the policies and procedures in place at each participating institution and according to the laws in the state where the informed consent is being signed. The original consent form will be placed in the medical record. A copy will be given to the participant and a copy will be filed with the research record.

7.0 **CRITERIA FOR EVALUATION AND ENDPOINT DEFINITIONS**

7.1 **Evaluable Patients**

Aim 1 (Survey): A subject will be considered evaluable if they complete the survey item indicating HPV vaccine initiation/non-initiation and for whom medical record abstraction data is submitted as described in Section 4.3.

Aim 2 (Vaccine Evaluation): A subject will be considered evaluable for the primary (immunogenicity) aim if they are seronegative for HPV-16 and/or HPV-18 at baseline, complete all 3 HPV vaccine doses within the specified administration windows (Section 5.4.4), have evaluable Month 7 Anti-HPV 4cLIA (for patients enrolled on or before 3-1-16) or 9cLIA (for patients enrolled after 3-1-16) results that were drawn within the acceptable window (Section 5.4.6), and for whom medical record abstraction data is submitted as described in Section 5.3. Safety data will be reported on all eligible subjects who receive at least one dose of vaccine, regardless of whether they are evaluable for the additional study aims.

7.2 **Primary Endpoints**

Aim 1 (Survey):

1. HPV vaccine non-initiation

Aim 2 (Vaccine Evaluation):

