8.0 STATISTICAL METHODS

8.1 Sample Size

Aim 1 (Survey): A sample size of 1090 eligible subjects is required to address Specific Aim 1. We have chosen this sample size based on our preliminary study (Section 2.9), from which we can assume that 90% (n=981) of those approached will participate in the survey. A sample of 981 survey participants for Specific Aim 1 will provide 80% power to reject the null hypothesis that the prevalence (p) of HPV vaccine initiation is ≤ 0.4 if the true p is at least 0.44 (one-sided test, Type I error=0.05). It will also provide a 2-sided 95% confidence interval (CI) of sample $p \pm .061$ if true $p=0.4$.

[Protocol v3, 8/17/15: Accrual goal for Aim 1 met, enrollment to survey closed]

Aim 2 (Vaccine Evaluation):

qHPV Vaccine Cohort (patients enrolled on or before 3-1-16): Based on national vaccine initiation rates and our preliminary data (Section 2.9),⁴⁰ we conservatively assume that 60% (n=589) of the 981 survey participants will have not initiated the HPV vaccine. Based on our data (Section 2.9) and prior trials,^{30,31,135} we conservatively assume that of the non-vaccinated survey participants, 60% (n=353) will agree to receive the vaccine, 96% (n=339) will be seronegative at baseline (Intent to Treat [IT] sample), and 92% (n=312) will complete all 3 doses, yielding 312 (Per-Protocol [PP]) subjects who will have received all 3 doses of qHPV vaccine for examining Aim 2.1. This sample size was calculated using the mean GMT and SD reported by Merck & Co.²⁸ for healthy males and females aged 9-15 years and 16-26 years as the historical healthy population. The following assumptions were made: i) cancer survivors were similarly distributed in regard to immunogenicity with the same SD as in this healthy population; ii) margin of equivalence (E) was $\frac{1}{2}$ of the mean GMT of the healthy population (Table 7). Using the method of Korn and Freidlin¹³⁶ for sample size calculations using historical controls, a total of 312 subjects (72 younger females, 77 older females, 82 younger males, and 81 younger males) will provide 80% power to demonstrate non-inferiority with respect to anti-HPV-16, and/or -18 GMT in cancer survivors compared to the healthy population assuming a one-sided t-test, Type I error =0.00312 (for an overall Type I error =0.025), and margin of equivalence (E) shown in Table 7 by sex and age for each vaccine type.

Table 7. Sample Size for Aim 2 (Vaccine Evaluation)

		Females								

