Anti-HPV	9-15y (younger)					16-26y (older)				
	Healthy	Cancer	E	SD	N	Healthy	Cancer	E	SD	N
16	4918.5	2459.3	2459.25	5585.26	72	2411.3	1205.65	1205.65	2915.77	77
18	1042.6	521.3	521.30	1161.91	69	475.6	237.80	237.80	500.01	58
		Males								
16	6056.5	3028.3	3028.25	6895.81	72	2401.5	1200.75	1200.75	2747.45	72
18	1357.4	678.7	678.70	1641.08	82	402.6	201.30	201.30	489.9	81

Sample size required = 312

The coordinating center will track enrollment to each stratum (Younger Females, Older Females, Younger Males, Older Males), and will close enrollment to each stratum once the targeted number of evaluable participants has been reached.

9vHPV Vaccine Cohort (patients enrolled after 3-1-16): Results of interim data analysis on the qHPV vaccine cohort (performed in January 2016 with data from patients who had a Month 7 sample available for analysis on or before 8-28-15; N=133) indicate that the cohort enrolled on or before 3-1-16 (N=254) who have received/are receiving the qHPV vaccine will be more than sufficient to address non-inferiority (i.e., lower limit of the multiplicity-adjusted 95% confidence intervals for the ratio of the mean geometric mean titer for anti-HPV-16 and -18 in the cancer vs. healthy population >0.5 for each

age/gender group) of the qHPV vaccine in cancer survivors. We are therefore extending the study to evaluate non-inferiority of the 9vHPV vaccine; interim data analysis results from the qHPV vaccine cohort indicate that an additional 200 patients will be sufficient to perform this evaluation in cancer survivors.

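### The 80% power stated for adverse-event comparisons in 8.2.2.3 belongs to superseded per-protocol sizes; neither the 254-patient qHPV cohort nor the 200-patient 9vHPV cohort delivers it

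*Combined protocol and SAP*

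**What the plan says.** Section 8.2.2.3 opens the AE analysis with "In the IT sample, the number of vaccine-associated AE within 7 (for 9vHPV) or 14 (for qHPV) days of each dose", compared with rates reported for the age- and sex-matched general population by chi-square or exact tests at Type I error 0.05 per comparison. It then gives differences detectable with 80% power at true rates 0.01 and 0.85, all for per-protocol sizes: 0.0485 and 0.1068 for 72 young females, 0.0415 and 0.1021 for 82 young males, and "For the entire PP sample of 312, the corresponding differences are 0.0189 and 0.0534".

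The sizes 72, 82 and 312 come from the qHPV calculation in 8.1 and Table 7. The later 9vHPV text in 8.1 moves to two cohorts. For qHPV it refers to "the cohort enrolled on or before 3-1-16 (N=254", and for 9vHPV it says that "an additional 200 patients will be sufficient to perform this evaluation in cancer survivors".

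On the analysis set, the only description of the IT sample is a label in the 8.1 recruitment forecast: "96% (n=339) will be seronegative at baseline (Intent to Treat [IT] sample". Section 7.1 says "Safety data will be reported on all eligible subjects who receive at least one dose of vaccine". It adds that this applies "regardless of whether they are evaluable for the additional study aims". Section 8.2.2.3 also has a separate line, "Overall cohort: % of subjects who discontinue vaccine related to AE".

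**The concern.** Safety and tolerability form one of the two primary endpoints listed for Aim 2 in 7.2, and 9.1 says that the vaccine's safety profile in cancer survivors is unknown. The power statement in 8.2.2.3 tells a reader how large an excess a non-significant AE comparison could have missed. The AE windows in that section were updated for the two cohorts, but the sample sizes beneath them were not. A reader would credit each cohort with 80% power for a 1.9- or 5.3-point difference when each has fewer patients than 312.

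The set named for the comparison also differs from the safety set in 7.1. A programmer following the only written meaning of IT would drop vaccinees for a positive baseline serology, which has nothing to do with safety. AE percentages could then appear on two denominators.

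**Working it through.** **Inputs.** From 8.2.2.3: reference rates 0.01 and 0.85, Type I error 0.05, 80% power, and the six stated differences. From 8.1: cohort sizes 254 and 200, and the chain 353 vaccinated, 339 seronegative, 312 completing. Sidedness is not stated and was inferred from what reproduces the plan.

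**Method.** One-sample exact binomial test against a fixed rate p0. The critical count c is the smallest value with P(X ≥ c | n, p0) ≤ a. The detectable difference d solves P(X ≥ c | n, p0 + d) = 0.80. For a two-sided 0.05 test, a = 0.025 at p0 = 0.85. At p0 = 0.01 the lower rejection region is empty for these sizes, so a = 0.05.

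**Step 1: reproduce the plan.**

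| n | c at 0.01 | d at 0.01 | c at 0.85 | d at 0.85 | Stated |
|---|---|---|---|---|---|
| 72 | 3 | 0.0485 | 68 | 0.1068 | 0.0485 / 0.1068 |
| 82 | 3 | 0.0415 | 77 | 0.1021 | 0.0415 / 0.1021 |
| 312 | 7 | 0.0189 | 278 | 0.0534 | 0.0189 / 0.0534 |

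All six values match, so the plan's arithmetic is correct for the sizes it names.

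**Step 2: the cohorts in 8.1, same method.** Power is evaluated at the stated n=312 differences, that is P(X ≥ c) at rates 0.01 + 0.0189 = 0.0289 and 0.85 + 0.0534 = 0.9034.

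| n | c (0.01 / 0.85) | d (0.01 / 0.85) | Power at 0.0189 / 0.0534 |
|---|---|---|---|
| 254 | 6 / 228 | 0.0209 / 0.0606 | 74.5% / 67.0% |
| 200 | 6 / 181 | 0.0292 / 0.0685 | 52.0% / 53.0% |

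The n=200 figure at rate 0.01 is inflated by discreteness. At n=198 the critical count is 5, the attained alpha is 0.050 and d = 0.0237. At n=200 the critical count is 6, the attained alpha falls to 0.016 and d = 0.0292.

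**Step 3: a smoother check.** The normal approximation solves d√n = 1.96√(p0(1−p0)) + 0.8416√((p0+d)(1−p0−d)).

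| n | d (0.01 / 0.85) | Power at 0.0189 / 0.0534 |
|---|---|---|
| 312 | 0.0190 / 0.0537 | about 80% / 80% |
| 254 | 0.0215 / 0.0591 | 74% / 70% |
| 200 | 0.0247 / 0.0660 | 67% / 57% |

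Relative to 312, d is 13% / 10% larger at 254 and 30% / 23% larger at 200.

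**Step 4: is per-protocol versus IT or all-dosed the cause?** No. The exact method gives 0.0200 / 0.0528 for the planned IT set (339) and 0.0189 / 0.0513 for all planned vaccinees (353), close to the stated 0.0189 / 0.0534. The loss comes from the move to two smaller cohorts.

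**Step 5: effect of the serostatus label on AE rates.** 353 − 339 = 14 planned vaccinees, or 4%. Assume an AE rate of 0.85 in the 339 and between 0.50 and 1.00 in the 14. The whole-cohort rate is then between (339×0.85 + 14×0.50)/353 = 0.8361 and (339×0.85 + 14×1.00)/353 = 0.8559, a shift of −1.4 to +0.6 percentage points. One event in an omitted person is 1/353 = 0.28 points.

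**The case against.** **No decision depends on these figures.** 8.2.2.3 sets no margin or pass rule for AE rates, and the stopping rule in 9.4 counts events. This stands and limits the importance of the point; what is at stake is how the safety results are read.

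**The cohorts might be pooled.** Section 8.2.2.1 requires separate evaluation only under immunogenicity. Pooling gives 254 + 200 = 454, where the normal approximation detects 0.0154 / 0.0450, better than stated. But the vaccines differ and 8.2.2.3 itself sets AE windows of 7 and 14 days, which points to analysis by cohort. If pooling is intended, the plan should say so.

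**The power figures depend on the method.** With 1.645 in place of 1.96, the normal approximation gives 79% (n=254) and 73% (n=200) at rate 0.01, so the n=200 value ranges from 52% to 73%. The 1.645 version gives 84.5% at n=312, so it does not reproduce the plan. The loss at 0.85 is less method-dependent, but in absolute terms the detectable difference grows only by 0.0606 − 0.0534 = 0.0072 and 0.0685 − 0.0534 = 0.0151.

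**The IT label may be loose wording.** It is a parenthesis in a qHPV recruitment forecast, nothing equivalent exists for 9vHPV, and 7.1 already states the safety set. This largely stands. The separate overall-cohort line does not settle it either, since it may only mean not split by age and sex. A reader might infer that seropositive vaccinees vanish from safety reporting or that the AE results would be materially biased. The documents do not support that: 7.1 keeps these participants in the safety report, and Step 5 shows a small effect.

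**Conclusion.** The point holds as a correction to the power statement. The stated differences are right for 312 but not for the cohorts now in 8.1. At those differences, exact power is about 75% / 67% in the qHPV cohort and 52% / 53% in the 9vHPV cohort, with the n=200 value at rate 0.01 being imprecise. It would be wrong to infer that the plan miscalculated, or that the shortfall comes from the serostatus restriction.

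The conclusion assumes analysis by cohort, a fixed historical rate as in the plan's own calculation, and that all 254 and 200 are dosed. If 200 is instead an evaluable target, applying the plan's qHPV proportions gives 200/(0.96 × 0.92) = 226 dosed, still below 254.

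The mismatch between the IT sample and the 7.1 safety set is a real inconsistency in the text. It is secondary and small in effect.

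**What to change.** In 8.2.2.3, replace the detectable differences for 72, 82 and 312 with values for each cohort's dosed set (254 qHPV and 200 9vHPV if all are dosed), stating the test and its sidedness. Because exact power moves in steps with n, give the critical count or attained alpha beside each figure. Add stratum values once stratum sizes are known; 8.1 gives none for the current cohorts. For illustration only, an equal split (assumed) of 50 per stratum for 9vHPV would give 0.0737 / 0.1192, and about 63 for qHPV would give 0.0568 / 0.1134.

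In the same section, replace the IT sample as the set for the AE comparison with the 7.1 safety set, so that no vaccinee is left out because of baseline serology.

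The cost is SAP wording and a population flag from data already collected, with no new visits or samples. The stated detectable differences become larger.

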1. HPV antibody titers (Anti-HPV 4cLIA [for patients enrolled on or before 3-1-16] or 9cLIA [for patients enrolled after 3-1-16] [Geometric Mean Titers; Seropositivity] (Day 1, Month 7, and Month 24) [Immunogenicity]
2. Vaccine Report Card (participant/parent diary of adverse events, collected for 7 days (for patients enrolled after 3-1-16) or 14 days (for patients enrolled on or before 3-1-16) following each vaccine dose, and Adverse Events/Research-Related Problems Reporting Forms [Safety/tolerability]

7.3 **Schema – Aim 1: Survey**

Aim 1: Survey

[Protocol v3, 8/17/15: Accrual goal for Aim 1 met, enrollment to survey closed]

Requirement	Pre-Entry	Study Entry
Verification of eligibility (Protocol Section 3.1)	X	
Informed consent/assent		X
Registration		X
Medical record abstraction: - Medical Record Review Form (Appendix 1) - Intensity of Treatment Rating Scale (Appendix 2)		X
Survey completion (Appendix 3)		X

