7.4 Schema – Aim 2:Vaccine Evaluation
Aim 2: Vaccine Evaluation

Requirement	Pre-entry	Day 1	Dose #2	Dose #3	Month 7	Month 24	PSD*
Verification of eligibility (Protocol Sections 3.2 and 3.3)	X						
Permission for participation from treating clinician	X						
Informed consent/assent		X					
Medical record abstraction: Cancer Treatment Summary Form (Appendix 7)					X		
Patient/parent education (Appendix 12, 13)		X	X	X			
Targeted review of systems Screening for acute illness Screening for pregnancy (if indicated) Vaccine Visit Form (Appendix 8)		X	X	X			
HPV Vaccine		Dose #1	Dose #2	Dose #3			
Vaccine Report Card (Appendix 14) x 7 days (if enrolled after 3-1-16) or 14 days (if enrolled on or before 3-1-16) post each vaccine dose, including home temperature monitoring 4 hours after each vaccine dose, then daily x 5 days		X	X	X			
Quantitative Ig [humoral immunity]		X					
Anti-HPV 4cLIA (if enrolled on or before 3-1-16) or 9cLIA (if enrolled after 3-1-16) [geometric mean titers and HPV type-specific seropositivity]		X			X	X	X
HPV-specific total immunoglobulin [qualitative aspects of HPV-specific humoral response]						X	
Adverse Events/Research-Related Problems Form (AERF; Appendix 15)		→	→	→	→	→	→
Month 7 Visit Form (Follow-Up #1) (Appendix 9)					X		
Month 24 Visit Form (Follow-Up #2) (Appendix 16)						X	
Premature Study Discontinuation (PSD) Form (Appendix 10) [†]							X

*PSD = Premature Study Discontinuation (collected at PSD clinic visit or when deemed lost to follow-up; see Section 5.4.12)

→ = AERF to be completed as needed at any study time point

[†]PSD Form will also be completed as needed at any time point that participation is terminated prematurely

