9.3 Adverse Events

9.3.1. Definitions

Adverse Event (AE) - An adverse event is any untoward medical experience or change of an existing condition that occurs during or after treatment, whether or not it is considered to be related to the protocol intervention.

Unexpected Adverse Event [21 CFR 312.32 (a) – An adverse event is unexpected if it is not listed in the investigator’s brochure and/or package insert; is not listed at the specificity or severity that has been observed; is not consistent with the risk information described in the protocol and/or consent; is not an expected natural progression of any underlying disease, disorder, condition, or predisposed risk factor of the research participant experiencing the adverse event.

Expected Adverse Event - Any event that does not meet the criteria for an unexpected event OR is an expected natural progression of any underlying disease, disorder, condition, or predisposed risk factor of the research participant experiencing the adverse event.

Serious Adverse Event (SAE) [21 CFR 312.32] - A serious adverse event (SAE) is defined as *any expected or unexpected adverse event* that results in any of the following outcomes:

- Death
- Is life-threatening (places the subject at immediate risk of death from the event as it occurred)
- Unplanned hospitalization (equal to or greater than 24 hours) or prolongation of existing hospitalization
- A persistent or significant disability/incapacity

- A congenital anomaly/birth defect
- Secondary malignancy, or
- Any other adverse event that, based upon appropriate medical judgment, may jeopardize the subject's health and may require medical or surgical intervention to prevent one of the outcomes listed above (examples of such events include allergic bronchospasm requiring intensive treatment in the emergency room or at home, blood dyscrasias or convulsions that do not result in inpatient hospitalization, or the development of drug dependency or drug abuse).

Unanticipated Problem (UP) – Any incident, experience or outcome that **meets all three** of the following criteria:

1. Unexpected (in terms of nature, severity, or frequency) given the following: a) the research procedures described in the protocol-related documents such as the IRB approved research protocol, informed consent document or Investigator Brochure (IB); and b) the characteristics of the subject population being studied; **AND**

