2. Related or possibly related to participation in the research (possibly related means there is a reasonable possibility that the incident, experience, or outcomes may have been caused by the drugs, devices or procedures involved in the research); **AND**
3. Suggests that the research places subjects or others at greater risk of harm (including physical, psychological, economic, or social harm) than previously known or recognized.

9.3.2. Reporting of Unanticipated Problems and Adverse Events:

Unanticipated Problems (UP): Unanticipated problems must be reported by the study coordinating center site personnel to the UAB DSMC and IRB within 5 calendar days of receiving notification from the participating sites according to definitions and guidelines at <http://www.uab.edu/policies/content/Pages/UAB-RA-PRO-0000293.aspx>. Any unanticipated problem that occurs during the study conduct will be reported to the DSMC and the central (UAB) IRB.

Serious Adverse Events (SAE) - All SAEs occurring during this study, whether observed by the physician, nurse, or reported by the patient, will be reported according to definitions and guidelines at <http://www.uab.edu/policies/content/Pages/UAB-RA-PRO-0000293.aspx> and Table 9.3.1 below. Those SAEs that require expedited reporting will be submitted via fax or electronic transmission.

Adverse Events (AE) - Adverse events will be monitored by the PMT. Adverse events that do not meet the criteria of serious OR are not unanticipated problems will be reported only in the protocol continuation reports and PMT report (see Table 9.3.1 below).

Table 9.3.1. Adverse Event and Unanticipated Problem Reporting Timelines for the DSMC and IRB

Required Reporting Timeframe to DSMC		
Attribution	UNEXPECTED	EXPECTED
	Death while on active treatment or within 30 days of last day of treatment	
Possibly, Probably, Definitely	5 calendar days	
Unlikely, Unrelated	5 calendar days	
	Death after 30 days of last active treatment/therapy	
Possibly, Probably, Definitely	5 calendar days	No reporting required*
Unlikely, Unrelated	No reporting required*	No reporting required*
	Grades 3 and 4 AND meeting the definition of “serious”	
Possibly, Probably, Definitely	5 calendar days	5 calendar days
Unlikely, Unrelated	5 calendar days	5 calendar days
	Grade 1 and 2 AND resulting in hospitalization#	
Possibly, Probably, Definitely	5 calendar days	10 calendar days
Unlikely, Unrelated	10 calendar days	10 calendar days

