9.3.3. Toxicity Management

Any symptoms that occur will be managed according to good medical practices and clinical judgment of the site investigator. Toxicities related to the vaccine will be monitored using the *Toxicity Grading Scale for Healthy Adult and Adolescent Volunteers Enrolled in Preventive Vaccine Clinical Trials*, U.S. Department of Health and Human Services, Food and Drug Administration, Center for Biologics Evaluation and Research, September 2007 (Tables 9.3.2, 9.3.3, and 9.3.4). Toxicities will generally be considered potentially vaccine-associated if their onset occurs within 7 days after receipt of a study vaccine dose. If evaluated, the toxicity should be documented on the Adverse Events/Research-Related Problems Reporting Form (AERF) within 2 working days of the evaluation. All subjects will be followed for the reporting of toxicities for 14 days following each vaccine dose. In addition, any severe or unexplained toxicity occurring after the 14 days of follow-up brought to the attention of the investigator will be evaluated for possible vaccine-association, and documented on the AERF within 2 working days of the evaluation if found to be possibly, probably, or definitely related to the vaccine. Toxicities will not be considered vaccine-associated AEs if clearly recognized alternative etiologies are identified. Alternative explanations for clinical abnormalities must be sought prior to study vaccine discontinuation.

Therapeutic interventions that may interfere with evaluation of the safety/tolerability of the vaccine should be avoided during the indicated timeframes unless medically necessary. These include a) any live attenuated vaccine administered within 28 days of any HPV vaccine dose; b) any subunit or killed vaccines (e.g., influenza, pneumococcal, antigen injections for allergy treatment) within 14 days of any HPV vaccine dose.

General toxicity management:

- If a subject develops a persistent \geq Grade 3 clinical toxicity, the subject will not be permitted to participate in this study until the toxicity has resolved to \leq Grade 1.
- All \geq Grade 3 clinical toxicities occurring within 14 days following any vaccine dose, and their

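### The only planned comparison of serious adverse events is limited to vaccine-associated events within 7 or 14 days of a dose, and no full-period SAE analysis is specified for Aim 2c

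*Combined protocol and SAP*

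**What the plan says.** Section 8.2.2.3 sets the safety analysis for Aim 2c. Its first sentence says that "the number of vaccine-associated AE within 7 (for 9vHPV) or 14 (for qHPV) days of each dose will be compared" to figures for the age- and sex-matched general population. The items that follow under that sentence are injection-site AEs, systemic AEs and the percentage "of subjects with serious AEs (e.g., life-threatening, result in persistent disability or death"). Two conditions therefore apply to SAEs in the comparison: the event must be vaccine-associated, and it must fall within 7 or 14 days of a dose.

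Later in the same paragraph: "AEs will be summarized descriptively as frequencies and percentages by type (injection site, systemic, serious), by vaccine dose" and across all doses. No period is given for this summary.

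Collection is much wider than the comparison:
- Section 7.2 defines the safety endpoint as the 7- or 14-day diary "and Adverse Events/Research-Related Problems Reporting Forms [Safety/tolerability"].
- Section 7.4 shows the report form (AERF) running through to Month 24: "AERF to be completed as needed at any study time point".
- Section 9.3.2: "All SAEs occurring during this study, whether observed by the physician, nurse, or reported by the patient, will be reported".
- Section 9.3.3 requires evaluation of "any severe or unexplained toxicity occurring after the 14 days of follow-up" that comes to the investigator's attention, and an AERF if it is judged at least possibly related.
- Section 9.3.1 counts "A congenital anomaly/birth defect" and secondary malignancy as SAEs.

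**The concern.** A 7- or 14-day window suits reactions recorded in a diary of the same length. It does not suit serious events, whose definition in 9.3.1 includes kinds that are rarely or never recognised so soon after an injection. The protocol expects related late events, since 9.3.3 sets up their evaluation, but the SAE comparison has no place for them.

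Hypothesis 2 states that the vaccines will be safe in survivors. Section 9.1 calls the safety profile in this group unknown, and 6.2 warns that side effects not yet known could occur. A windowed SAE percentage near zero could be offered in support of the hypothesis while related late SAEs sit in the database without a prespecified table. Because the descriptive summary has no stated period, two analysts could also report different SAE percentages from the same data.

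**Working it through.** **The plan's own figures.** The only figures in 8.2.2.3 are detectable differences in AE rates, and all six reproduce with an exact one-sample binomial test. At a rate of 0.01, with 0.05 in the upper tail, the rules are at least 3/72, 3/82 and 7/312, and power at the stated differences is 0.800, 0.800 and 0.799. At a rate of 0.85, with 0.025 in the upper tail, the rules are at least 68/72, 77/82 and 278/312, and the 80%-power differences are 0.1068, 0.1021 and 0.0534. This point does not rest on them; they show no arithmetic error.

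**Inputs for the window share.**
- Window per dose: 7 days (9vHPV) or 14 days (qHPV), from 8.2.2.3. Three doses give 3 × 7 = 21 or 3 × 14 = 42 days.
- Dose 3: weeks 24-32 after Dose 1 (Table 5).
- Month 7: 4-8 weeks after Dose 3 (Table 6), so weeks 28-40, or 196-280 days from Dose 1.
- Month 24: the note in 5.4.11 and Table 6 give 72-84 weeks after Dose 3, so weeks 96-116, or 672-812 days. The heading of 5.4.11 gives 72-84 weeks after Dose 1, or 504-588 days. Both are carried through.

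**Share of follow-up covered = window days ÷ follow-up days.**

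| Follow-up from Dose 1 | 9vHPV | qHPV |
|---|---|---|
| To Month 7 (196-280 days) | 21/280 to 21/196 = 7.5-10.7% | 42/280 to 42/196 = 15.0-21.4% |
| To Month 24, timed from Dose 3 (672-812 days) | 21/812 to 21/672 = 2.6-3.1% | 42/812 to 42/672 = 5.2-6.3% |
| To Month 24, timed from Dose 1 (504-588 days) | 21/588 to 21/504 = 3.6-4.2% | 42/588 to 42/504 = 7.1-8.3% |

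**Share of SAEs outside, if the rate were constant.** This is one minus the share covered. To Month 24 it runs from 1 − 0.083 = 92% to 1 − 0.026 = 97%. To Month 7 it runs from 1 − 0.214 = 79% to 1 − 0.075 = 92.5%.

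**How far clustering after doses would change this.** Half of the SAEs fall inside the windows when the inside rate is (follow-up − window) ÷ window times the outside rate.
- To Month 24 timed from Dose 3: 651/21 = 31 to 791/21 = 38 for 9vHPV; 630/42 = 15 to 770/42 = 18 for qHPV.
- To Month 24 timed from Dose 1: 483/21 = 23 to 567/21 = 27 for 9vHPV; 462/42 = 11 to 546/42 = 13 for qHPV.
- To Month 7: 175/21 = 8 to 259/21 = 12 for 9vHPV; 154/42 = 3.7 to 238/42 = 5.7 for qHPV. Clustering matters more over this shorter period.

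**Three events traced through the text.**
- Hospitalisation 20 days after Dose 2, rated possibly related: reported under 9.3.2, outside both windows.
- Pregnancy in the vaccine phase, infant with an anomaly: an SAE under 9.3.1. Doses stop and the outcome is followed (9.3.4), but a birth outcome will essentially never fall within 14 days of a dose.
- Hospitalisation on day 10 after a 9vHPV dose: inside the 14-day toxicity follow-up that 9.3.3 sets for all subjects, outside the 7-day comparison window.

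The vaccine-associated filter narrows the comparison further. Section 9.3.3 generally treats a toxicity as potentially vaccine-associated when its onset is within 7 days, so an unattributed SAE can fail the filter as well as the window.

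**The case against.** The window governs one sentence, the comparison with the general population. The descriptive sentence later in the paragraph names serious events and sets no window. Section 9.2 sends the percentage of subjects with SAEs to the monitoring committee, also without a window, at least every six months. All SAEs go to the manufacturer regardless of causality (9.3.2.1.2). Section 7.1 promises safety data on every eligible subject given a dose. A reader might infer from 8.2.2.3 that late SAEs are discarded, or can never enter the safety result. The documents do not say that, and this part of the objection stands.

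A fixed window can also be right for an external comparison, which needs the same observation period on both sides. That stands too, so the windowed figure should be kept where the reference uses a matching window.

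On size, a reader might infer that most SAEs are lost. The documents give no SAE counts or timing, and the windowed quantity is limited to vaccine-associated events, which can be expected to cluster after doses. The 92-97% is therefore conditional on a constant rate. Pregnancy outcomes do have their own reporting route (9.3.4), much secondary malignancy in this population will be background, and no safety comparison between the two vaccine cohorts is planned.

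The gap remains after all this. The descriptive sentence is organised by dose, follows the windowed one and can be read either way; it does not say where an SAE at Month 18 belongs. Committee reports are monitoring, not the prespecified Aim 2c result.

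**Conclusion.** The point holds as a limit on the SAE comparison combined with an unspecified full-period analysis. Followed as written, 8.2.2.3 keeps related late SAEs, and 9vHPV SAEs on days 8-14, out of the only SAE comparison. It leaves the period of the descriptive SAE summary open, although the endpoint in 7.2 includes report forms that run to Month 24.

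The share of follow-up covered is firm arithmetic: about 7.5-21% to Month 7 and 3-8% to Month 24, depending on cohort, visit timing and the Month 24 anchor. The share of SAEs missed is not firm: 92-97% to Month 24 needs a constant event rate, which the documents neither state nor support. The immunogenicity results are unaffected. What is at risk is how the safety conclusion in Hypothesis 2 is supported.

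**What to change.** In 8.2.2.3:
- Keep the 7/14-day window for injection-site and systemic diary reactions, and for any external SAE comparison whose reference uses a matched window.
- Add the percentage of subjects with any SAE from Dose 1 to Month 7 and from Dose 1 to end of study, overall and by attribution, in the 7.1 safety population (all eligible subjects with at least one dose).
- Include the late related toxicities that 9.3.3 already documents.
- Take SAEs from the AERF and also from the non-expedited quarterly and PMT reports. Section 9.3.2.1.1 ties AERF submission by sites to events needing expedited reporting, and Table 9.3.1 exempts some deaths more than 30 days after last treatment, so the AERF alone could miss deaths.
- State the period of the descriptive SAE summary.

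Two sets of passages must be reconciled: the 7-day 9vHPV window in 8.2.2.3 with the 14-day follow-up of all subjects in 9.3.3, and the Month 24 anchor in the heading of 5.4.11 with its note and Table 6.

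The cost is SAP wording and one or two table rows, with no new data collection. The small downside is that the SAE percentage will be higher and will include unrelated events, so it must be shown by attribution.
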